3.2.3.6.10 End of Study Visit

While the exact timing for the end of the study is unknown and depends on the accumulation of a sufficient number of fracture events, it is estimated to be approximately 3 years after the end of enrollment. The SPONSOR will alert sites when the study will be terminated. At that point, all patients must be brought in for a final visit. Laboratory safety assessment, biomarkers and archive samples do not need to be obtained if less than 30 days have elapsed since the last collection. DXA scans do not need to be performed if less than 6 months have elapsed since the last scan was performed.

Product: MK-0822

24

Protocol/Amendment No.: 018-04

Sites will be asked to contact all patients by telephone to schedule the End of Study visits and to re-enforce the importance of this visit. Every effort should be made to ensure that all patients attend the End of Study Visit in the time pre-specified by the SPONSOR.

Table 3-8 lists the procedures to be performed at the final study visit.

Table 3-8

List of End of Study Procedures

Perform BMD at the total hip (and subregions) and lumbar spine [§] ^{††} Perform BMD at the distal forearm and total body [¶] Complete PE (including vital signs, height and weight) Perform lateral spine x-ray [§] Collect blood and urine for laboratory safety assessment [†] Collect blood and urine for lab efficacy assessment and archives [‡] Administer calcium questionnaire [#] Review diary card Perform tablet count for compliance (only for blinded study therapy) Review Adverse Experiences Concomitant Medication Review Perform Health Resource Utilization (if fracture has occurred) Plasma for proteomics archive

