3.4.5.2 Selected Nonserious Adverse Experiences

These selected non-serious experiences are also known as Events of Clinical Interest (ECI) and must be recorded as such on the Adverse Experience Case Report Forms/Worksheets.

Product: MK-0822

38

Protocol/Amendment No.: 018-04

Events of clinical interest for this trial include:

Persistent elevations [$> 3 \times$ Upper Limit of Normal (ULN)] in aspartate aminotransferase (AST) or alanine aminotransferase (ALT) (2 consecutive readings at least 2 weeks apart) or persistent elevations [$> 2 \times$ Upper Limit of Normal (ULN)] in total bilirubin (2 consecutive readings at least 2 weeks apart) as determined by way of protocol-specified laboratory testing or unscheduled laboratory testing.*

***Note:** These criteria are based upon available regulatory guidance documents. The purpose of the criteria is to specify a threshold of abnormal hepatic tests that may require an additional evaluation for an underlying etiology.

Rash and Skin AEs

During the phase IIb trial for odanacatib, the SPONSOR received information regarding an ongoing assessment of a cutaneous safety signal observed with the use of a non-Merck cathepsin K inhibitor balicatib [5]. The adverse experience has been described as “morphea-like, local skin thickening.” For that reason, serious or severe rash and adverse experiences suggestive of morphea will be closely monitored in the odanacatib program. All serious skin AEs, or severe (according to intensity rating) skin AEs, or skin AEs with skin thickening and hardening suggestive of morphea or systemic sclerosis will be promptly reported (within 24 hours) as Events of Clinical Interest. In the reporting of these adverse experiences, all associated information that is considered relevant (e.g. medical history, concomitant therapy, the appearance, distribution, and duration of the rash, any treatments employed, dermatology consultation notes generated, the results of any procedures performed as part of the work-up, and if available, photographs of the lesion, etc.) should be completely documented and submitted with the patient data. Skin cancers are not considered ECIs. In addition, the skin AEs with skin thickening and hardening suggestive of morphea or systemic sclerosis will undergo adjudication.

Skin AEs that do not meet the criteria for ECIs above (i.e. those that are non-serious, and non-severe, or not suggestive of morphea) will follow standard data entry cycle times.

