In addition, the percentage of patients who experienced a stature loss of greater than 1 cm during the study will be tabulated. A logistic model will be used to compare the two treatment groups, including terms for treatment, geographic region and stratum. The model-based odds ratio, and 95% confidence interval, will be provided as an estimate of the treatment effect.

The rate of stature loss will also be examined, using a mixed model with fixed effects for treatment, geographic region, stratum, treatment-year interaction and random intercept and slope (year). The within patient serial correlation of the values over time will be modeled by an unstructured covariance matrix. The magnitude of the slopes (rate of stature loss) will be summarized from the model, as well as the difference between treatments (mean and 95% CI). More detail on this mixed model is in appendix 6.7.

Bone Mineral Density Endpoints

For each body site and timepoint, BMD will be summarized at baseline and follow-up, by the mean and standard error, together with the mean percent change from baseline and its 95% confidence interval.

The percent change from baseline in BMD endpoints at all during-treatment time points will be analyzed using a longitudinal model with fixed effects for treatment, stratum, geographic region, and treatment-by-time interaction¹. The within patient serial correlation of the values over time will be modeled by an unstructured covariance matrix. More detail on this longitudinal model is in appendix 6.7.

The treatment effect at each of the on-treatment time points will be assessed by evaluating the within- and between-treatment group Least-Squares means (LS mean) and the associated 95% confidence intervals. Treatment difference will be tested at each of the on-treatment time points and adjustment for multiple testing will be handled as discussed below.

Similar analyses will be performed in the subgroup of bisphosphonate-intolerant patients (defined as patients with a contraindication or history of intolerance to bisphosphonates, or those considered by their physician to be unsuitable for bisphosphonate treatment).

A graphical presentation of the LS mean (+/-SE) change from baseline over time will also be provided.

Biochemical Markers

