Results of the health resource utilization questionnaire will be summarized at each of the during treatment time points and overall, by means of number (%) of patients who received medical care for a fracture since the last visit and the number (%) patients who received each of the types of medical care (physician or other healthcare professional office, emergency room visit, hospital admission, nursing home or rehabilitation hospital admission, physical therapy clinic visit).

In addition, although originally not foreseen in the protocol, event rates for each type of medical care visit will also be summarized overall and by time point for each treatment group, for all types of visits combined and by type of medical care visit. The event rate will be calculated as the number of patients with at least one medical care visit (per type) divided by the number of patient-years of follow-up.

Furthermore, the number and percent of patients who experienced each type of medical care by fracture type will also be summarized.

Results of the meal questionnaire will be summarized at Months 3, 6, and 9, for the patients of the "Lead Cohort".

Product: MK-0822

51

Protocol/Amendment No.: 018-04**Major Cardiovascular and Cerebrovascular Events**

Time to first major cardiovascular and cerebrovascular event will be summarized in tabular and graphical format by the Kaplan-Meier method and estimation of the hazard ratio.

Population PK

Population PK analysis and/or PK/PD modeling may be performed. Details will be specified in a separate population PK/PD Statistical Analysis Plan.

Genetic Markers

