The “All Patients-as-Treated” (APaT) approach will be used, which includes all patients who were randomized to double-blind treatment and received at least one dose of study medication. For this analysis patients will be counted in the treatment group for the treatment they actually received: if patients received one dose of the medication they were randomized to, they will be considered in their randomization treatment group, only if they received none of their actual randomization treatment and received the other treatment they will be considered in the other treatment group.

For vital signs and laboratory safety endpoints the APaT approach will be used, including all patients who took at least one dose of double-blind study medication and had a baseline and on-treatment measurement. Missing data will not be imputed.

Clinical Safety

Summary statistics will be provided for the change from baseline at each on-treatment time point in weight, blood pressure and pulse rate, by treatment group. Height will be handled as an efficacy endpoint.

Laboratory Safety

The primary focus of laboratory data will be based, for each laboratory test, on the proportion of patients exceeding predefined limits of change from baseline and/or exceeding predefined values, at least once during treatment period, until 14 days after the last dose of double-blind treatment.

The predefined limits of change from baseline and predefined values are displayed in Table 1.

For those predefined limits characterizing a large increase from baseline and/or a large on-treatment value, a patient exceeding the predefined limit will be classified as “above limit.” For those predefined limits characterizing a large decrease from baseline and/or a low on-treatment value, a patient exceeding the **predefined limit will be classified** “below limit.” The proportion of patients exceeding the predefined limits will be presented for the treatment groups, together with the 95% confidence intervals on the difference between the treatments.

In addition to the analysis of predefined limits of change, the change from baseline at each of the on-treatment time points in laboratory tests will be summarized for each of the treatment groups. No tests will be performed on the laboratory data.

A listing of all laboratory tests performed is in the appendix.

Product: MK-0822

18

Protocol/Amendment No.: 018-04

Table 1

Predefined Limits of Change Definitions for Laboratory Tests

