Month 39 (1,187)	1,142 to 1,232	-
Month 42 (1,278)	1,233 to 1,324	-
Month 45 (1,370)	1,325 to 1,415	-
Month 48 (1,461)	1,416 to 1,506	-

If the study continues beyond Year 4, additional timewindows will be defined similarly.
[†] Meal questionnaire was only performed in the ~1,500 Lead Cohort patients.
[‡] Provided measurement was not more than 30 days after the last dose of treatment in the complete study.

Product: MK-0822

30

Protocol/Amendment No.: 018-04

Table 7

Relative Day Ranges for Safety Analyses
Clinical Safety and Laboratory Endpoints

Time Point (Target Day)	Blood Pressure, Heart Rate APaT Analysis	Weight APaT Analysis	Laboratory Tests APaT Analysis
Baseline (1)	-90 to 1	-60 to 1	-90 to 1
Month 3 (91)	2 to 137 [†]	2 to 137 [†]	2 to 137 [†]
Month 6 (183)	138 to 228 [†]	138 to 228 [†]	138 to 228 [†]
Month 9 (274)	229 to 319 [†]	229 to 319 [†]	229 to 319 [†]
Month 12 (365)	320 to 456 [†]	320 to 425 [†]	320 to 456 [†]
Month 18 (548)	457 to 639 [†]	488 to 608 [†]	457 to 639 [†]
Month 24 (731)	640 to 822 [†]	671 to 791 [†]	640 to 822 [†]
Month 30 (913)	823 to 1,004 [†]	853 to 973 [†]	823 to 1,004 [†]
Month 36 (1,096)	1,005 to 1,187 [†]	1,036 to 1,156 [†]	1005 to 1,187 [†]
Month 42 (1,278)	1,188 to 1,369 [†]	1,218 to 1,338 [†]	1,188 to 1,369 [†]
Month 48 (1,461)	1,370 to 1,552 [†]	1,401 to 1,521 [†]	1,370 to 1,552 [†]
APaT: All-Patients-as-Treated.			
[†] Provided measurement was not more than 14 days after the last dose of treatment in the complete study.			

For all endpoints, except morphometric vertebral fractures, in the event that a variable has more than one value in a day range, the value closest to the target day of the time window will be selected for the FAS analysis. If a patient has 2 values on this day, the mean of these 2 values will be taken for the analysis. For the per protocol approach, the measurement closest to the target day in the day range, which does not violate the protocol violation criteria will be selected.

For morphometric vertebral fractures, all available scans will be used to determine the presence of a fracture in a time window, not only the scan closest to the target day.

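### The closest-to-target rule is stated too broadly: it drops End of Study heights and fracture-care forms that two whole-period endpoints need (minor)

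*Protocol*

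**What the plan says.** The text after Table 7 in Protocol Appendix 6.7 sets the selection rule: "For all endpoints, except morphometric vertebral fractures, in the event that a variable has more than one value in a day range, the value" that is "closest to the target day of the time window will be selected for the FAS analysis". The next sentences average two values taken on the same day and give a matching rule for the per-protocol approach. One exemption is stated, for morphometric vertebral fractures, where "all available scans will be used to determine the presence of a fracture in a time window".

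Two other FAS endpoints are not defined at a time point.

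- **Stature.** Section 3.5.5.1 says "the percentage of patients who experienced a stature loss of greater than 1 cm during the study will be tabulated". Table 3-8 in Section 3.2.3.6.10 requires a closing height ("Complete PE (including vital signs, height and weight"). DXA is waived at that visit if the last scan is less than six months old; height has no such waiver. Table 3 of Appendix 6.7 sets the height windows. Its footnote keeps measurements more than 30 days after the last dose out of the main analysis but allows them in a supportive one.
- **Fracture care.** Section 3.5.5.1 summarises the "number (%) of patients who received medical care for a fracture since the last visit". The form is repeated at End of Study for women who have had a fracture, and Table 6 sets the windows.

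For laboratory tests, Appendix 6.7 counts patients who exceed a predefined limit "at least once during treatment period, until 14 days after the last dose of double-blind treatment". This uses the APaT population, with windows in Table 7.

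**The concern.** One value per window is right when the estimand is a mean at Month 24 or Month 36. It is wrong for an outcome that asks whether something ever happened, or what happened over an interval. The plan recognises this for vertebral films by using every film in a window, but extends the exemption to nothing else.

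For height, the value at risk is the last one, when cumulative loss is expected to be greatest. For the care form, two forms in one window are not competing measurements of one quantity: they report on different intervals, so dropping either deletes the only record of the care in its interval. The same-day averaging step has no sensible meaning for yes/no care items, which suggests the rule was written with continuous measurements in mind.

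The stakes are an undercount in one analysis of a secondary endpoint and in one descriptive exploratory endpoint.

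**Working it through.** The plan gives no figure for this effect, so there is none to reproduce. The protocol also gives no event rates for these endpoints, so the check is on the windows.

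**Inputs.** Height window for Month 36 (Table 3): target day 1,096, days 914 to 1,278. Care-form window for Month 36 (Table 6): target day 1,096, days 1,051 to 1,141. The windows in each table are contiguous. Visit window: ±3 weeks (Section 1.7). Assumption: the close-out date is uniform between consecutive scheduled visits.

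**Simple count, scheduled visit exactly on target**

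- Height: an End of Study height on days 1,097 to 1,278 shares the Month 36 window and is farther from target, so it is dropped. That is 182 of the 364 days before the Month 48 target: 50%. From day 1,279 it falls in the Month 48 window and is kept.
- Care form: days 1,097 to 1,141 are lost, 45 of the 90 days before the Month 39 target: 50%.

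**Allowing for visit variation.** Let the scheduled visit fall e days from target, e uniform on (−21, 21), and let close-out follow x days later, x uniform over a cycle of C days. The half-window is L = C/2. The closing value is dropped if e + x ≤ L and |e + x| > |e|. For either sign of e, the qualifying range of x has length L − |e|, and the mean of |e| is 10.5.

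- Height (C = 365, L = 182.5): (182.5 − 10.5)/365 = 172/365 = 0.471.
- Mean gap between the kept and the dropped height: (L² − E[e²]) / (2 × (L − 10.5)), with E[e²] = 21²/3 = 147. This gives (33,306 − 147)/(2 × 172) = 96 days.
- Final care form (C = 91, L = 45.5): (45.5 − 10.5)/91 = 35/91 = 0.385.
- Last scheduled care form, dropped when it was early and the closing form is nearer the target: ½ × (2 × 10.5)/91 = 0.115.

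**Effect on the 1 cm endpoint.** Average observation lost per woman is 0.471 × 96 ≈ 45 days. Over four years (1,461 days) that is 45/1,461 = 3.1%. Over three years it is 45/1,096 = 4.1%, and over five years 45/1,826 = 2.5%. If losses first pass 1 cm at a constant rate, these are also the shares of such losses missed. A rate that rises late in follow-up would make the share larger.

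**The case against.** The case for leaving the text alone has several parts, and most of them limit the point without removing it.

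- **Height.** The change at each yearly time point and the slope model properly need one value per window. Only the 1 cm proportion is harmed, and a programmer could treat its whole-study definition as governing. The Table 3 footnote already removes late off-drug heights from the main analysis, so the 47–50% applies only to heights within 30 days of the last dose. This stands as a limit on size. But the rule covers all endpoints with one named exception, so following it literally still gives the wrong count.
- **Care form.** It is completed only by women with a fracture, is exploratory and untested, and no window is stated for the overall summary. All true. The by-time-point tables are still caught, and the wording does not exempt the overall count.
- **Laboratory limits.** A reader might infer that unscheduled, for-cause values are discarded from the limit counts. The documents do not support that. The selection sentences name only the FAS and per-protocol analyses, whereas laboratory data are APaT. The at-least-once definition is specific and can use every value, with the Table 7 windows serving the separate change-from-baseline summaries. Section 3.4.5.2 also captures qualifying hepatic results "as determined by way of protocol-specified laboratory testing or unscheduled laboratory testing", through adverse-experience reporting that has no day windows. What remains is ambiguity: the rule refers to all endpoints directly beneath Table 7, and no APaT selection rule is given.

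**Conclusion.** The point holds for two endpoints and is minor. As written, the rule drops about 47–50% of End of Study heights taken within 30 days of the last dose, and about 38% of final and 12% of last scheduled care forms among women with a fracture. These shares rest on a uniform close-out date and on visits spread evenly within ±3 weeks. The consequence for stature loss above 1 cm is about 3% of such losses missed, assuming a constant rate and about four years of follow-up.

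A reader might take the loss of nearly half the closing heights to mean that the endpoint is badly compromised or biased towards one arm. Neither follows. The retained annual height is only about three months older on average, and selection depends on calendar timing rather than on treatment or outcome. The expected result is a small undercount and some lost precision.

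No primary endpoint is affected: vertebral films are exempt, and clinical fractures are analysed as time to event. For laboratory limits, only a clarification is warranted.

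**What to change.** In Appendix 6.7, limit closest-to-target selection to by-time-point summaries and to the longitudinal and slope models. Then state that:

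1. stature loss above 1 cm uses every valid height including End of Study, subject to the existing 30-day footnote in the main analysis, with all heights used in the supportive analysis;
2. all care questionnaires in a window are combined, with care recorded as yes if any form says yes;
3. for clarity, laboratory predefined-limit counts use all scheduled and unscheduled values up to 14 days after the last dose.

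The cost is a few sentences and small programming changes, made before unblinding for the final analysis. No new data are needed.
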